# **6.2 Analysis Methods**

### Primary end-point analysis

The Kaplan Meier method will be used to estimate cumulative mortality rate over the 12-month follow-up. The survival rate will be compared using the log-rank test.

Hazard ratio for death (rifaximin group vs. control group) and its 95% confidence interval will be determined using a Cox proportional hazard model. In this model, a center effect will be tested as well as interaction between treatment and center. The assumption of proportional hazards will be tested using Schoenfeld residuals and if violated, the model will be fitted with a treatment- time interaction or a time-varying covariate, as appropriate.

The mortality rate at 12 months will be described according to age, sex, and specific liver scores (Child-Pugh and MELD) to examine their potential effects. Each of these factors will be analyzed statistically using a Cox proportional hazard model incorporating terms for treatment, the covariate and the treatment-by-covariate interaction.

The number of dead patients, estimated treatment effect hazard ratios, and associated 95% confidence intervals will be calculated within each of the subgroups generated by these analyses.

Covariate n	No. Deaths	Treatment effect HR - 95%CI	P value
Intervention			
Placebo		Ref	
Rifaxim		Treatment effect	
Subgroup analyses			
Age			
<median< td="">	<median effect<="" td="">	</median>	</median<>		<median effect<="" td="">	</median>	
>median		>median effect	—
Sex			
Male		Effect in men —	
Female	I AO	Effect in women	
Child Pugh score			
В		Effect in B patients —	
С		Effect in C patients —	
Child Pugh score		Â	
<median< td="">	<median effect="" td="" —<=""></median>	</median<>		<median effect="" td="" —<=""></median>	
>median		>median effect —	

Sensitivity analyses

Analysis of the primary endpoint will be repeated after exclusion of patients with a suspicion of AAH and a Maddrey score  $\geq$  32 points.

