### Secondary objectives:

Demonstrate the effectiveness of rifaximin compared to placebo in reducing:

- Hospital mortality rate and mortality rate at 3 and 6 months
- Incidence of spontaneous ascites fluid infection at 12 months
- Incidence of other complications of cirrhosis (hepatorenal syndrome, gastrointestinal hemorrhage, hepatic encephalopathy) at 12 months
- Number of days spent in hospital during the follow-up period
- Analyze the safety of the drug under study
- Analyze the composition of the gut microbiota in 25 patients in each group (day 1, months 3, 6, 12 and 18).
- To show that rifaximin significantly decreases (compared to placebo) serum levels of IL-6, lipopolysaccharides (LPS), copeptin, von Willebrand factor antigen and CRP between J1 and J30.

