# **Section 4: Statistical Principles**

# 4.1 Confidence Intervals and P-values

The interim analysis was performed when about 70% of the expected information is available (112 patients with complete follow-up), with a significance boundary p-value of 0.01. Consequently, the final analysis will have to be performed with a significance boundary **p-value of 0.043**.

All other tests will be two-sided, with p values of 0.05 or less denoting statistical significance. 95% confidence interval will be used to report effect estimates of secondary endpoints.

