# **5.3 Baseline Patient Characteristics**

The description and initial comparison of randomized groups will focus on the demographic characteristics, clinical features of liver disease, previous complications of cirrhosis, and pre-existing treatment. Past medical history, concomitant treatments and biological results will also be compared.

Quantitative variables will be in the form of a table showing the number of values and the number of missing data, the mean and median, standard deviation, coefficient of variation, the minimum and maximum for each group and for the overall population.

Categorical variables will be in the form of a table revealing the number of values and the number of missing data, the percentage of each category and the confidence intervals for each group and for the overall population.

Continuous variables will be compared using Student's t-test or the Mann-Whitney test, as appropriate. Categorical variables will be compared using the Chi-squared test or Fisher's exact test, as appropriate.

The description will include the following variables:

Age, years Sex Weight, kg BMI, kg/m^2

Comorbidities

- Type 2 diabetes
- Hypertension
- Severe acute alcoholic hepatitis (Maddrey score  $\geq$  32)
- Hepatocellular carcinoma within Milan criteria
- Alcohol consumption
- Daily alcohol consumption if not abstinent, g

Cause of liver cirrhosis

- Alcohol
- Hepatitis B / B Delta
- Hepatitis C
- MAFLD (=NASH)
- Other

Child Pugh score

MELD score

Liver parameters

- Alanine aminotransferase, UI/L
- Aspartate aminotransferase, UI/L
- Gamma glutamyl transferase, UI/L

- Alkaline phosphatase, UI/L
- Bilirubin, µmol/L
- Platelet count, G/L
- International normalized ratio
- Prothrombin index
- Albumin, g/L
- Creatinine, µmol/L
- Baseline CRP
- CRP Day 30
- Difference between baseline and Day 30 CRP

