### Secondary end-points analysis

Hospital survival and, 3- and 6-month survival

The hospital survival will be estimated from the proportion of patients discharged alive. Proportions will be compared between the two groups using Chi-square test. Odds ratios for hospital death and 95% confidence intervals will be estimated by using logistic regression.

The 3-month and 6-month survival rates will be compared with the same methods as described above for mortality rate at 12 months.

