#### Variations of IL-6, LPS, copeptin, CRP, vWF antigen in serum between day 1 and day 30.

Differences in IL-6, LPS, copeptin, CRP, vWF antigen serum values between day 1 and day 30 will be calculated and difference means in each treatment group will be compared with Student's t-test or the Mann-Whitney test, as appropriate.

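### SAP section 6.2 subtracts the day 1 biomarker value but does not adjust for it, which is valid but gives up precision; it should also say that the reported hazard ratio does not include the treatment-by-centre terms

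*SAP*

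**What the plan says.** **Biomarkers.** One secondary objective in Section 2 reads "To show that rifaximin significantly decreases (compared to placebo) serum levels of IL-6", and goes on to lipopolysaccharides, copeptin, von Willebrand factor antigen and CRP, over the first 30 days. Section 6.1 defines the endpoint as the variation of each marker between day 1 and day 30. Section 6.2 forms each patient's difference and states that "difference means in each treatment group will be compared with Student's t-test", with the Mann-Whitney test as the alternative. No model contains the day 1 value as a covariate. Section 4.1 sets the level for these tests: "All other tests will be two-sided, with p values of 0.05 or less denoting statistical significance". The baseline list in section 5.3 also includes "Difference between baseline and Day 30 CRP", so the change is tabulated for that marker as well.

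**Centre terms.** In section 6.2 the log-rank test compares survival. For the hazard ratio, "its 95% confidence interval will be determined using a Cox proportional hazard model". The text continues: "In this model, a center effect will be tested as well as interaction between treatment and center". It names no test statistic and does not say what follows from the result. The next sentence does state what will be done if the proportional-hazards check fails. The table shell in the same section has a single overall treatment row above the subgroup rows.

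**The concern.** The biomarker objective is worded as something to be shown at a significance level, so precision matters. Subtracting day 1 fixes the slope of day 30 on day 1 at exactly 1. When the true slope is below 1, as is usual for a noisy marker, the difference over-corrects and carries extra variance from the day 1 measurement. Adjusting for day 1 estimates the slope from data the trial already collects. What is at stake is power and interval width for five secondary endpoints, not bias.

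On centre, the model that supplies the hazard ratio is also the one in which the interaction is tested, and the SAP leaves the consequence open. A model that retained treatment-by-centre terms would have no single treatment hazard ratio. The test itself rests on very few deaths per centre and arm.

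**Working it through.** **Biomarkers.** The SAP gives no SD, correlation or power for any marker, so it has no figure to reproduce. Let r be the correlation between the day 1 and day 30 values and k the ratio SD(day 30)/SD(day 1). Both are assumed.

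In units of the day 1 variance, the per-patient variance behind the treatment contrast is:

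- change score: 1 + k² − 2rk
- analysis of covariance: k²(1 − r²)
- ratio: k²(1 − r²)/(1 + k² − 2rk)

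| k | r = 0.3 | r = 0.5 | r = 0.7 |
|---|---|---|---|
| 0.8 | 0.5824/1.16 = 50% | 0.48/0.84 = 57% | 0.3264/0.52 = 63% |
| 1 | 0.91/1.4 = 65% | 0.75/1.0 = 75% | 0.51/0.6 = 85% |
| 1.25 | 1.4219/1.8125 = 78% | 1.1719/1.3125 = 89% | 0.7969/0.8125 = 98% |

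The change-score variance minus the covariance-analysis variance is 1 − 2rk + r²k² = (1 − rk)². This cannot be negative, so on a common scale the ratio never exceeds 1. It equals 1 only when the slope rk is exactly 1. This is the large-sample result; estimating the slope costs one degree of freedom.

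At k = 1, 80 patients per arm analysed as change carry the information of 80 × 0.65 = 52, 80 × 0.75 = 60 or 80 × 0.85 = 68 per arm analysed with the covariate.

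A simulation gives the power at k = 1 (10,000 runs, normal data on one scale, an assumed 70 per arm with both samples, a true effect of 0.357 SD):

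| | r = 0.3 | r = 0.5 | r = 0.7 |
|---|---|---|---|
| t-test on change | 43% | 54% | 77% |
| Covariance analysis | 59% | 67% | 84% |

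With no true effect both reject in 4.8 to 5.2% of runs, so both are valid. These figures compare against the t-test, not the Mann-Whitney option.

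The endpoint is preserved. Writing Y for day 30, X for day 1 and T for treatment, Y − X = a + bT + cX is the same model as Y = a + bT + (1 + c)X. The coefficient b is identical.

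**Centre terms.** Inputs: 80 per arm, 12-month survival of 40% and 60%, 10% dropout (section 3.3), and 17 centres (Section 2).

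- Deaths without dropout: 80 × 0.6 + 80 × 0.4 = 80.
- Constant hazards: −ln 0.4 = 0.916 for placebo, −ln 0.6 = 0.511 for rifaximin, −ln 0.9 = 0.105 for dropout.
- Placebo deaths: 80 × (0.916/1.022) × (1 − 0.4 × 0.9) = 45.9.
- Rifaximin deaths: 80 × (0.511/0.616) × (1 − 0.6 × 0.9) = 30.5.
- Total: about 76, or 76/(17 × 2) = 2.2 per centre and arm.
- Interaction degrees of freedom: 17 − 1 = 16.

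With no true interaction and a nominal 5% level, simulation of this design (2,000 trials per setting) gave rejection in 16 to 25% of trials for the likelihood-ratio test. The Wald test rejected in about 0.3 to 0.6% with equal centres and 2.4 to 2.8% with unequal centres. Block size (2, 4 or 6) and centre sizes (9 to 10 each, or 19 down to 2) are assumptions. The answer therefore depends heavily on a statistic the SAP does not name.

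**The case against.** The case for leaving the plan alone has several parts.

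- **The biomarker comparison is valid and does use day 1.** This is correct. A reader might infer that the baseline value is ignored or the comparison biased. It is neither, because day 1 is subtracted and allocation is randomised. The loss is of precision only, on secondary endpoints, and it depends on correlations the SAP does not give. At k = 1.25 and r = 0.7 it is 2%.
- **The SAP says the centre terms are tested, not kept.** This also stands. The single overall treatment row in the table shell points to one hazard ratio without interaction, though it does not settle whether a centre main effect stays in. A reader might infer that the interaction could alter the primary result. The primary p-value comes from the log-rank test, so it cannot. What remains is an unreliable test with no stated consequence.
- **The 3- and 6-month analyses.** Survival at those times "will be compared with the same methods as described above for mortality rate at 12 months". A reader might take this to repeat the centre tests on even fewer deaths. It may equally mean only the log-rank comparison, so no claim is made here.
- **MELD.** A reader might count the lack of a single MELD-adjusted hazard ratio as a defect. It is not one: the unadjusted analysis is valid, and MELD already enters a Cox model "incorporating terms for treatment, the covariate and the treatment-by-covariate interaction". A further adjusted estimate would be a matter of preference.

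**Conclusion.** The biomarker point holds as a recommended gain in efficiency, not as an error. For assumed correlations of 0.3 to 0.7, adjusting for day 1 reduces the variance by 15 to 35% at equal SDs, 37 to 50% when the day 30 SD is 0.8 of the day 1 SD, and 2 to 22% when it is 1.25 times as large. In large samples the gain is never negative on a common scale. It rests on the day 1 sample preceding the first dose; section 5.3 calls the CRP value baseline, which fits this. Both analyses use the same patients, those with both samples, because section 6.3 excludes imputation.

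The centre point is a minor clarification. With about 2 deaths per centre and arm, the 16-degree-of-freedom test should not influence which hazard ratio is reported. The documents do not show that it would; they only fail to say that it will not. Neither point touches the log-rank test, its 0.043 boundary or the validity of any planned comparison.

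**What to change.** **Biomarkers, section 6.2.** Replace the two-sample comparison with an analysis of covariance for each marker: change from day 1 to day 30 regressed on treatment and the day 1 value, reported with its 95% confidence interval. Use the log scale for both the change and the covariate if the marker is skewed. Choose the scale on pooled data without treatment codes, before database lock. The endpoint in section 6.1 remains a change.

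**Centre terms, section 6.2.** Add one sentence: the reported hazard ratio and its confidence interval come from the Cox model without the treatment-by-centre interaction, and treatment-by-centre is descriptive only.

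**Cost.** SAP wording only. No new data, no added patients, and no change to the primary test or its significance level. The one real downside is interpretive: a log-scale result is a ratio between arms, not an absolute difference in concentration.

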### Secondary end-points analysis

Hospital survival and, 3- and 6-month survival

The hospital survival will be estimated from the proportion of patients discharged alive. Proportions will be compared between the two groups using Chi-square test. Odds ratios for hospital death and 95% confidence intervals will be estimated by using logistic regression.

The 3-month and 6-month survival rates will be compared with the same methods as described above for mortality rate at 12 months.

#### Incidence of SBP during follow-up

The cumulative risk of SBP during follow-up in each group will be estimated by calculating the cumulative incidence function (CIF) of SBP at 12 months. The association of treatment group with SBP hazard function will be tested using univariate and multivariate Fine-Gray models. In this approach, death free of SBP during follow-up will be considered as a competing event.

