# 3.3 Sample size

The sample size is estimated based on a projected 40% survival rate at 12 months in the placebo group and 60% in the rifaximin group and a dropout rate of 10% at 12 months. In order to be able to detect any noticeable survival benefit in the rifaximin arm early in the trial, one interim analysis will be conducted. The significance boundaries of the interim and the final analyses were determined using a flexible alpha spending function (specifically alpha time (t2) spending function). This method ensures an alpha nominal risk inferior to 0.05 for the whole analysis.

We calculated that 160 patients (80 per group) would yield an 85% power in a two-sided test of hypothesis. The interim analysis will be performed when about 70% of the expected information is available (112 patients with complete follow-up), with a significance boundary p-value of 0.01. Consequently, the final analysis will have to be performed with a significance boundary p-value of 0.043. The estimated alpha nominal risk using these critical values will be 0.048. All sample size calculations were performed using PASS 14 software.

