#### **Exclusion criteria**

- Pregnant or breastfeeding woman
- Vulnerable person under French law
- Individual under legal protection measure
- Individual unable to express their consent
- Person under 18 years of age and over 80 years of age
- Transplanted patients, HIV infection (or patients who deny HIV serology) or immunosuppressive therapy (including patients under corticosteroids for severe alcoholic hepatitis if the patients respond to steroids with improvement of liver function)
- Patients with a liver transplant project and an estimated waiting time for liver transplantation of 3 months or less
- History of SBP
- Any present bacterial infection
- Patient who have received a TIPS procedure before the randomization
- Patients with an alfapump® system (added in protocol V5)
- Patient receiving antibiotics (including rifaximin) in the 7 days preceding the inclusion in this study except for patients participating to the microbiota study (15 days).
- Hypersensitivity to rifaximin, derivatives of rifamycin or one of the constituents of the preparation
- Hepatocellular carcinoma outside the Milan criteria, other cancer at a palliative stage
- Any clinical situation with a very low short-term prognosis (other than cirrhosis), i.e. a survival estimated lower than one month (added in protocol V5)
- Gastrointestinal bleeding within 7 days
- Intestinal obstruction
- Grade 3 hepatic encephalopathy (HE) during the previous 6 months before randomization
- Chronic heart failure (stage III or IV of the New York Heart Association [NYHA] Functional Classification)
- Patient judged as noncompliant
- Patients who cannot receive a clear information and who have no trusted relatives
- Patient who refuses the participation agreement by signing the information form and consent as defined in the protocol.
- Exclusion period from another biomedical study

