### 5.2 Withdrawal/Follow-up

Criteria for stopping the study are:

• withdrawal of consent,

- liver transplantation,
- loss to follow up
- enrollment of ineligible subjects.

Patients withdrawn from the study for withdrawal of consent, liver transplantation or loss to follow up will be censored at the date of withdrawal. Ineligible subjects will be excluded from the mITT analyses.

For all other patients, monitoring of the patient will continue, follow-up will focus on collecting the endpoints of the trial:

- vital status,
- date of death,
- complications of liver cirrhosis (HE, gastrointestinal bleeding and HRS),
- dates and length of hospital stays during the 12 months following inclusion in the trial

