#### Incidence of the other complications of liver cirrhosis during follow-up

The other complications (HE, gastrointestinal bleeding and HRS) will be analyzed as a composite event (the date of occurrence being the one of the first diagnosed complication) as well as separate events. The cumulative risk of other complications during follow-up in each group will be estimated by calculating the CIF at 12 months. The association of treatment group with the hazard function of other complications will be tested using univariate and multivariate Fine-Gray models. In this approach, death free of complications during follow-up will be considered as a competing event.

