### Survival analysis

All patients not reaching the primary endpoint at the end of follow-up or before their last assessment (for patients lost to follow-up) will be censored at the date of their last assessment visit. Patients receiving a liver transplant will be censored at the time of liver transplantation.

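### The cumulative-incidence and Fine-Gray analyses of SBP and other complications count only death as competing and censor liver transplantation, so they estimate risk as if transplant did not occur, which the SAP neither states nor justifies

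*SAP*

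**What the plan says.** Section 6.2 of the SAP plans a 12-month cumulative incidence function (CIF) for SBP in each arm and then a regression: "The association of treatment group with SBP hazard function will be tested using univariate and multivariate Fine-Gray models". The only competing event named is death: "In this approach, death free of SBP during follow-up will be considered as a competing event". The other complications (HE, gastrointestinal bleeding and HRS, as a composite and separately) follow the same scheme: "In this approach, death free of complications during follow-up will be considered as a competing event".

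Transplantation is dealt with elsewhere. Section 5.2 makes it a criterion for stopping the study and puts it in one rule with consent withdrawal and loss to follow-up: "Patients withdrawn from the study for withdrawal of consent, liver transplantation or loss to follow up will be censored at the date of withdrawal". That rule is not tied to any one endpoint. The next sentences keep endpoint collection going only for the remaining patients: "For all other patients, monitoring of the patient will continue, follow-up will focus on collecting the endpoints of the trial". Section 6.3, under its survival-analysis heading, repeats the handling: "Patients receiving a liver transplant will be censored at the time of liver transplantation".

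Transplants during follow-up are possible by design. Among transplant candidates, the exclusion criteria remove only "Patients with a liver transplant project and an estimated waiting time for liver transplantation of 3 months or less", so those with a longer expected wait can enter and be followed for 12 months.

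**The concern.** A competing-risks method is chosen so that patients who can no longer be observed to have the event are not handled as if they were merely lost. The SAP applies that reasoning to death but not to transplantation, which also ends observation of the patient and replaces the cirrhotic liver in which these complications arise.

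A censored patient's remaining weight passes to the patients still under follow-up. The CIF therefore answers the question of what the risk would be if nobody were transplanted, and it does so on the assumption that transplanted patients would have had the same later risk as those who stayed. Neither the target nor the assumption is written down, and no sensitivity analysis addresses either. A reader of the trial report would naturally take the 12-month CIF as the proportion of patients who actually had SBP or the complication, and it would be somewhat higher than that.

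**Working it through.** **Coding that follows from the text.** Section 6.2 gives the event of interest code 1 and event-free death code 2. Section 5.2 censors transplant (code 0) for all endpoints. An analyst who follows the SAP exactly has no other option, so this is a stated rule and not missing detail.

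**Inputs.** The SAP gives no SBP, complication or transplant rate, so there is no stated figure to reproduce. From section 3.3: "projected 40% survival rate at 12 months in the placebo group and 60% in the rifaximin group". Assumed, not in the SAP: constant hazards that act independently; SBP hazard s = 0.3 per year in both arms (no SBP effect); 12-month transplant probability t = 5%, 10% or 20%, meaning the probability if no other event intervened.

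**Hazards per year.**
- Death: placebo d = -ln(0.40) = 0.916; rifaximin d = -ln(0.60) = 0.511.
- Transplant: u = -ln(1 - t) = 0.051, 0.105, 0.223.

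**Formula.** 12-month CIF = s/(s + d + u) × [1 - exp(-(s + d + u))]. With transplant censored, the estimator targets u = 0.

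- Placebo, censored: 0.3/1.216 × (1 - 0.296) = 17.4%.
- Placebo, competing, t = 20%: 0.3/1.439 × (1 - 0.237) = 15.9%.
- Rifaximin, censored: 0.3/0.811 × (1 - 0.444) = 20.6%.
- Rifaximin, competing, t = 20%: 0.3/1.034 × (1 - 0.356) = 18.7%.

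| Arm | Censored | Competing, t = 5% | t = 10% | t = 20% | Excess (points, from unrounded values) |
|---|---|---|---|---|---|
| Placebo | 17.4% | 17.0% | 16.6% | 15.9% | 0.4, 0.7, 1.5 |
| Rifaximin | 20.6% | 20.1% | 19.6% | 18.7% | 0.5, 0.9, 1.9 |

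Rifaximin has the higher incidence here only because fewer patients die first. Over a wider assumed grid (censored CIF 10% to 30%, the same t), the excess runs from 0.2 to 2.6 points, about 2% to 10% in relative terms.

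**Treatment comparison.** The subdistribution hazard ratio is approximated by ln(1 - F_rifaximin)/ln(1 - F_placebo) at 12 months.
- No SBP effect, s = 0.3: 1.21 censored; 1.20 with transplant competing at any of 5%, 10% or 20% in both arms.
- SBP hazard 0.35 in placebo and half that on rifaximin: 0.612 censored; 0.611, 0.610 and 0.608 competing at 5%, 10% and 20% in both arms.
- Same hazards, unequal transplant: 0.58 with 5% placebo and 15% rifaximin; 0.64 with 15% placebo and 5% rifaximin.

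**If censoring is not independent.** The closed form assumes independence. A simulation (400,000 patients, placebo death hazard, SBP hazard 0.35) let a shared frailty raise each patient's SBP, death and transplant hazards together. At t = 5%, 10% and 20%, the transplant-censored CIF was 17.2%, 17.1% and 16.9%. The incidence actually occurring was 17.0%, 16.5% and 15.8%, and the true no-transplant risk was about 17.3% throughout. As transplants become more common, the censored estimate drifts away from both targets.

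**The case against.** The strongest reply is that this is a choice of estimand and not an error. Censoring at transplant is explicit, it matches the primary analysis, and complication risk without transplant is a recognisable quantity. That would stand if the SAP named it as the target and defended the independence it needs. It does neither, and a 12-month CIF that already lets death compete points towards the incidence that actually occurs.

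The second reply is size, and most of it stands. The stated aim is a comparison with placebo, and the subdistribution hazard ratio hardly moves with equal transplant rates. The visible shifts need an assumed 5% versus 15% split in a blinded trial. With 80 patients per arm, the standard error of a 17.4% incidence is √(0.174 × 0.826/80) = 4.2 points, so the largest placebo excess, 1.5 points, is about a third of it.

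The 20% scenario is also high beside the 10% dropout planned in section 3.3, if that figure includes transplants; the SAP does not say. Up to t = 10%, the excess is at most about 0.7 points (placebo) and 0.9 (rifaximin).

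Two stronger readings are tempting and should not be drawn:
- **That the sickest patients are the ones transplanted, so independent censoring is known to fail.** The SAP says nothing on who is transplanted. Independence is unsupported here, not disproved, and the frailty simulation is only one assumed pattern.
- **That transplant rules out every component exactly as death does.** The SAP does not limit gastrointestinal bleeding to a portal-hypertensive cause, so it does not show that bleeding becomes impossible afterwards. The case needs less: transplant ends observation and changes the later risk.

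**Conclusion.** The point holds as an unstated and unjustified target for secondary endpoints. Sections 5.2 and 6.2 together produce CIFs for SBP and the other complications that set transplantation aside, and as estimates of actual 12-month incidence they are modestly too high in each arm. The direction needs only that some transplants occur before the event and that patients still followed are representative. The size rests on rates not in the SAP: about 0.4 to 1.5 points for placebo and 0.5 to 1.9 for rifaximin, with an SBP hazard of 0.3 per year and 5% to 20% transplant. These figures are for SBP; with no rates for HE, bleeding or HRS, no separate estimate is offered for them.

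A reader might infer that the treatment effect on SBP is materially biased. The calculations do not support that unless transplant frequency differs between arms. Such a difference cannot be excluded in advance, since the design expects more rifaximin patients to be alive and so available for transplant. The primary mortality analysis is outside this point.

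**What to change.** In both parts of section 6.2 (SBP and other complications), define the competing event as death or liver transplantation, whichever comes first, before the event of interest. Code it that way in the CIFs and in the Fine-Gray models. State in section 5.2 or 6.3 that the transplant-censoring rule does not apply to these analyses. Report the number and timing of transplants by arm, so that a reader can judge whether the comparison is affected. Keep the transplant-censored version as a sensitivity analysis, labelled as the risk in the absence of transplant under independent censoring.

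The cost is a sentence in each of the two parts, one event code and one repeated analysis on secondary endpoints. No new data are needed, because transplant dates are already required for censoring. The reported incidences will be slightly lower.
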